1.1.2.1 Neoadjuvant Immunotherapy Treatment in Stage III Melanoma

Nonclinical studies demonstrated improved survival and increased anti-tumor immunity when immune CPI therapy was given before surgery as compared with adjuvant application (Liu et al. 2016; Brockwell et al. 2017; Bourgeois-Daigneault et al. 2018; Brooks et al. 2018; O'Donnell et al. 2019). Patients with clinically detectable Stage III melanoma are ideal candidates for neoadjuvant therapy because they represent a high-risk patient population with poor outcomes when treated with upfront surgery alone. Neoadjuvant therapy also has the advantage of providing information on pathologic response, which is valuable to estimate prognosis and to guide the choice of adjuvant therapy and follow-up (Tetzlaff et al. 2018). Moreover, the availability of tumor tissue before and following therapy enables efficient exploration of possible mechanisms of resistance and response as well as identification of baseline biomarkers. Neoadjuvant therapy for melanoma is now an active area of research, with numerous completed and ongoing trials that have disparate designs, endpoints, and analyses (Menzies et al. 2021). The International Neoadjuvant Melanoma Consortium (INMC) was created by

experts in medical oncology, surgical oncology, pathology, radiation oncology, radiology, and translational research who developed recommendations for investigating neoadjuvant therapy in melanoma to align future trial designs and correlative analyses (Amaria et al. 2019).

Six melanoma neoadjuvant trials were conducted recently with BRAF/MEK-targeted therapy or PD-1-based immunotherapy (reviewed by Amaria et al. 2019). These trials demonstrated that neoadjuvant therapies can achieve high pathologic complete response (pCR) rates and impressive RFS in Stage III melanoma (Menzies et al. 2021; Rozeman et al. 2021). The initial data are particularly promising for the neoadjuvant combination of nivolumab plus ipilimumab. Treatment with nivolumab plus ipilimumab results in pathologic response rates (pRRs) between 70%–80%, is well tolerated, and may reduce surgical morbidity (Rozeman et al. 2019; Blank et al. 2020).

This study protocol was developed in accordance with INMC guidelines to create the needed consistency amongst neoadjuvant trials in order to facilitate optimal data organization for future regulatory review. Its exploratory analysis plan will strengthen translational research across the melanoma disease continuum.

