Patients eligible for treatment beyond progression will be informed by the investigator that they may be foregoing other treatment options known to confer clinical benefit while continuing to receive the study treatment. Patients have the right to voluntarily withdraw from the study at any time for any reason. In addition, the investigator has the right to

withdraw a patient from the study for medical conditions that the investigator or Sponsor determines may jeopardize the patient's safety if he/she continues in the study.

If at a subsequent tumor assessment, pseudoprogression is ruled out and progression of the disease is confirmed, the patient will be discontinued from study treatment.

Figure 3 Detailed Study Schema (Cohort 1)

CLND=completion lymph node dissection; Comp.=completion; CT=computed tomography; Discon.=discontinuation; FU=follow-up; LT=long-term; M=month; R=randomization; Q3M=every 3 months; Tx=treatment; W=week.

^a At the discretion of the investigator, patients will start either adjuvant therapy or observation commencing in Week 13.

^b The Cycle 2 Day 1 on-treatment tissue sample must be collected up to 72 hours prior to drug administration.

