3.1.5 Assessments and Monitoring

All patients will be closely monitored for adverse events throughout the study. Adverse events will be graded according to the National Cancer Institute Common Terminology Criteria for Adverse Events, Version 5.0 (NCI CTCAE v5.0). CRS severity will also be graded according to the American Society for Transplantation and Cellular Therapy (ASTCT) CRS Consensus Grading Scale.

Patients in Cohort 1 will receive neoadjuvant treatment for 2 cycles (6 weeks) and will undergo surgery (CLND) in Week 7. All patients are expected to proceed with surgery, provided that there are no distant metastases and the surgeon considers the disease to be completely resectable. Pathologic response will be assessed locally and by independent pathologic review.

Patients who discontinue treatment due to unacceptable toxicity and continue to have no evidence of metastatic disease will still be eligible for surgery and proceed with CLND after the adverse event has resolved and re-staging confirms Stage III disease.

If patients have confirmed disease progression, patient management and treatment selection will be at the discretion of the treating physician. These patients will remain in the study for follow-up.

Patients will undergo radiological tumor assessments in Week 6 (from Day 1 of Cycle 1) prior to surgery (CLND) (see Section [4.5.7](#) for details). Response will be assessed and

determined by the investigator in accordance with RECIST v1.1, but confirmation by later imaging studies is not required (see [Appendix 1](#)).

Patients in Cohort 2 will undergo tumor assessments every 9 weeks (from Day 1 of Cycle 1) for the first 54 weeks and then every 12 weeks thereafter (see Section [4.5.7](#)). Response will be assessed by the investigator using RECIST v1.1 (see [Appendix 1](#)). Response per modified RECIST v1.1 for immune-based therapeutics (iRECIST) (see [Appendix 2](#)) will be determined programmatically by the Sponsor on the basis of investigator-assessed individual lesion data.

For Cohort 1 and Cohort 2, if clinical activity is demonstrated in an experimental arm, the Sponsor may request that tumor assessment scans for that arm and the corresponding control arm be submitted for evaluation by an independent review facility.

For all patients, blood samples will be collected at baseline and during the study for biomarker research, including blood-based next-generation sequencing (NGS) and circulating tumor DNA (ctDNA) testing.

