3.3 DURATION OF PARTICIPATION

In Cohort 1, the total duration of study participation for each individual from screening until the treatment completion visit and start of adjuvant treatment is expected to be approximately 17 weeks (not including long-term follow-up):

- Screening: Up to 4 weeks; Days –28 to –1
- Treatment period: 13 weeks; participants will receive neoadjuvant treatment during a 6-week period and will undergo surgery at Week 7. After surgery and prior to commencing adjuvant treatment, treatment completion will be performed in Week 13.

After the treatment period, participants may continue onto long-term follow-up:

- Information on long-term follow-up and new anti-cancer therapy (including targeted therapy and immunotherapy) will be collected by telephone, patient medical records, and/or clinic visits approximately every 3 months until death (unless the patient withdraws consent or the Sponsor terminates the study).

In Cohort 2, the total duration of study participation for each individual is expected to be up to 5 years:

- Screening: Up to 4 weeks; Days –28 to –1
- Treatment period: participants will continue to receive treatment until unacceptable toxicity or loss of clinical benefit as determined by the investigator after an integrated assessment of radiographic and biochemical data, local biopsy results (if available), and clinical status (e.g., symptomatic deterioration such as pain secondary to disease).
- Safety follow-up: 28 days after the last dose of treatment
- Long-term follow-up: Information on long-term follow-up and new anti-cancer therapy (including targeted therapy and immunotherapy) will be collected by telephone, patient medical records, and/or clinic visits approximately every 3 months until death (unless the patient withdraws consent or the Sponsor terminates the study).

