5.3.1 Adverse Events Reporting Period

Investigators will seek information on adverse events at each patient contact. All adverse events, whether reported by the patient or noted by study personnel, will be recorded in the patient's medical record and on the Adverse Event eCRF.

After informed consent has been obtained but prior to initiation of study treatment, only serious adverse events caused by a protocol-mandated intervention (e.g., invasive procedures such as biopsies, discontinuation of medications) should be reported (see Section 5.4.2 for instructions for reporting serious adverse events).

After initiation of study treatment, all adverse events will be reported until 30 days after the final dose of study treatment or until initiation of new systemic anti-cancer therapy, whichever occurs first, and serious adverse events and adverse events of special interest will continue to be reported until 135 days after the final dose of study treatment or until initiation of new systemic anti-cancer therapy, whichever occurs first.

Instructions for reporting adverse events that occur after the adverse event reporting period are provided in Section 5.6.

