5.4.2.2 Events That Occur after Study Treatment Initiation

After initiation of study treatment, serious adverse events and adverse events of special interest will continue to be reported until 135 days after the final dose of study treatment or until initiation of new systemic anti-cancer therapy, whichever occurs first.

Investigators should record all case details that can be gathered immediately (i.e., within 24 hours after learning of the event) on the Adverse Event eCRF and submit the report via the electronic data capture (EDC) system. A report will be generated and sent to Roche Safety Risk Management by the EDC system.

In the event that the EDC system is unavailable, the paper Clinical Trial Adverse Event/Special Situations Form provided to investigators should be completed and submitted to the Sponsor or its designee immediately (i.e., no more than 24 hours after learning of the event), either by faxing or by scanning and emailing the form using the

fax number or email address provided to investigators. Once the EDC system is available, all information will need to be entered and submitted via the EDC system.

Instructions for reporting serious adverse events that occur after the reporting period are provided in Section 5.6.

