6.5 SAFETY ANALYSES

Verbatim adverse event terms will be mapped to Medical Dictionary for Regulatory Activities thesaurus terms, and adverse event severity will be graded according to NCI CTCAE v5.0 and also according to the ASTCT CRS Consensus Grading Scale for CRS.

Safety will be assessed through summaries of adverse events, changes in laboratory test results, changes in vital signs and ECGs, and exposure to study drugs. Exposure to combination treatment and length of safety follow-up will be summarized by treatment arm.

All verbatim adverse event terms will be mapped to Medical Dictionary for Regulatory Activities thesaurus terms. Adverse event severity will be graded according to NCI CTCAE v5.0, and severity of CRS will also be graded by the investigator according to the ASTCT Consensus Grading (Lee et al. 2019). All adverse events, serious adverse events, adverse events leading to death, adverse events of special interest, and adverse events leading to study treatment discontinuation that occur on or after the first dose of study treatment (i.e., treatment-emergent adverse events) will be summarized by mapped term, appropriate thesaurus level, and severity grade. For events of varying severity, the highest grade will be used in the summaries. Deaths and causes of death will be summarized.

Relevant laboratory, vital sign (pulse rate, respiratory rate, blood pressure, pulse oximetry, and temperature), and ECG data will be displayed by time, with grades identified where appropriate. Additionally, a shift table of selected laboratory test results will be used to summarize the baseline and maximum postbaseline severity grade. Changes in vital signs and ECGs will be summarized.

Additionally, in Cohort 1, the incidence, nature of immune-related adverse events Grade ≥ 3 during the first 12 weeks, and the rate and duration of delayed surgery due to treatment-related adverse events will be summarized by treatment arm. CLND may be delayed for up to 2 weeks if study treatment-related adverse events have not improved sufficiently at the time of planned surgery (see Section 3.1.3).

Additionally, surgical complications will be scored according to Clavien-Dindo classification ([Appendix 5](#)). Complication rates for every grade will be reported and scored for patients that underwent CLND.

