Appendix 11: Study Details Specific to Nivo+Ipi Arm (Control)

Given the evidence of clinical efficacy in both the neoadjuvant and adjuvant settings, and the fact that nivolumab in combination with ipilimumab is approved for patients with advanced melanoma, combination treatment with nivolumab 3 mg/kg + ipilimumab 1 mg/kg was considered to be the best comparator for the anticipated patient population in this study (Wolchok et al. 2013; Sznol et al. 2014; Rozeman et al. 2019).

Nivolumab will be administered at a dose of 3 mg/kg IV and ipilimumab will be administered at a dose of 1 mg/kg IV Q3W on Day 1 of each 21-day cycle.

A11-4 MATERIALS AND METHODS SPECIFIC TO NIVO+IPI ARM

A11-4.1 TREATMENT IN NIVO+IPI ARM

A11-4.1.1 Formulation, Packaging, and Handling

A11-4.1.1.1 Nivolumab

The nivolumab drug product will be supplied by the Sponsor as a 10 mg/mL concentrate for solution for infusion.

For information on the formulation, packaging, and handling of nivolumab, refer to the local prescribing information for nivolumab.

A11-4.1.1.2 Ipilimumab

The ipilimumab drug product will be supplied by the Sponsor as a 5 mg/mL concentrate for solution for infusion.

For information on the formulation, packaging, and handling of ipilimumab, refer to the local prescribing information for ipilimumab.

A11-4.1.2 Dosage, Administration, and Compliance

Patients in the nivolumab + ipilimumab (Nivo+Ipi) control arm will receive treatment for 2 cycles (6 weeks) as outlined in [Table A11-1](#) until surgery, or until unacceptable toxicity or loss of clinical benefit, whichever occurs first (see [Section 3.1.2](#) for details). It is recommended that treatment be initiated no later than 7 days after randomization.

Table A11-1 Treatment Regimen for Nivo+Ipi Arm

Cycle Length	Dose, Route, and Regimen (drugs listed in order of administration)
21 days	
• Nivolumab 3 mg/kg IV on Day 1 of each cycle• Ipilimumab 1 mg/kg IV on Day 1 of each cycle

Ipi=ipilimumab; Nivo=nivolumab.

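### Cohort 1 SAE and AESI tables pool patients followed for 63–69 days with patients followed for 135 days after the last dose, with no common cut-off for comparing arms

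*Combined protocol and SAP*

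**What the plan says.** **Reporting rule.** Section 5.3.1 collects all adverse events to 30 days after the final dose. SAEs and AESIs go on "until 135 days after the final dose of study treatment or until initiation of new systemic anti-cancer therapy, whichever occurs first". Section 5.4.2.2 repeats this ("serious adverse events and adverse events of special interest will continue to be reported until 135 days after the final dose of study treatment", with the same early stop), and Section 5.6 defines the window in the same way. None of the three exempts adjuvant therapy.

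**Cohort 1 timeline.** "Patients in Cohort 1 will receive neoadjuvant treatment for 2 cycles (6 weeks) and will undergo surgery (CLND) in Week 7" (Section 3.1.5). All arms use 21-day cycles with dosing on Day 1; for the control arm, Appendix 11 states that "ipilimumab will be administered at a dose of 1 mg/kg IV Q3W on Day 1 of each 21-day cycle". Section 3.3 adds: "After surgery and prior to commencing adjuvant treatment, treatment completion will be performed in Week 13". The Figure 3 footnote in Section 3.1.2 reads: "At the discretion of the investigator, patients will start either adjuvant therapy or observation commencing in Week 13". Section 1.1.1.2 describes standard adjuvant treatment as anti-PD-1 or targeted therapy, and both are systemic.

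**After the window closes.** Section 5.6 keeps all deaths reportable. It also keeps open, with no end date, any SAE the investigator learns of and believes related to study treatment.

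**Analysis.** Section 6 summarizes results by treatment received. The Section 6.5 list includes SAEs and AESIs and finishes with "adverse events leading to study treatment discontinuation that occur on or after the first dose of study treatment". It fixes a start but no common end. Section 6.5 also summarizes length of safety follow-up by arm and, for Cohort 1, Grade ≥3 immune-related events in the first 12 weeks.

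**The concern.** A stop at new systemic therapy is a familiar way to keep toxicity of the next treatment out of the tables. In Cohort 1, however, that next treatment is a planned branch of the study, so the stop is a scheduled exit for an unknown share of patients. It ends causality-blind collection of SAEs and all collection of non-serious AESIs in patients who go on to adjuvant therapy, while patients on observation stay under full collection.

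A crude SAE or AESI percentage then mixes two lengths of observation. If the mix differs between arms, the arm with more patients on observation has more time in which late events can be recorded, and may look more toxic for that reason alone. These tables inform the benefit–risk reading of each arm, including the two 600 mg arms, which Section 3.1.2 enlarges to 40 patients in the preliminary phase to make that assessment more precise.

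**Working it through.** **Check of the plan's own timeline.** Surgery in Week 7 plus the 6 weeks to the completion visit (Section 4.6.1) gives Week 13, as stated. Four weeks of screening plus 13 weeks gives the stated 17 weeks.

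**Inputs.** Two 21-day cycles dosed on Day 1, so the final dose is on Day 22. Window length 135 days. Adjuvant start in Week 13. Week *w* covers Days 7(*w* − 1) + 1 to 7*w*, so Week 13 is Days 85–91.

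**Window per patient.** Full window end = 22 + 135 = Day 157. Truncated window = adjuvant start day − final dose day.

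| Patient | Days observed after last dose | Share of 135 |
|---|---|---|
| Observation | 135 | 100% |
| Two doses, adjuvant in Week 13 | 85 − 22 = 63 to 91 − 22 = 69 | 47–51% |
| Two doses, surgery 2 weeks late, adjuvant assumed in Week 15 (Days 99–105) | 77 to 83 | 57–61% |
| One dose only (Day 1), adjuvant in Week 13 | 84 to 90 | 62–67% |

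**Mean window per arm.** Mean = 135 − uptake × (135 − truncated window). Adjuvant uptake is not given in the documents, so it is an assumption. With a truncated window of 63–69 days:

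- 20% uptake: 121–122 days
- 50% uptake: 99–102 days
- 80% uptake: 77–82 days

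**Gap between arms.** Take a truncated window of 66 days, so each adjuvant patient loses 69. Compare a pathologic response rate (pRR) of 75%, the middle of the 70–80% cited in Section 1.1.2.1 for nivolumab plus ipilimumab, with an assumed 50%. Uptake in an arm = pRR × uptake in responders + (1 − pRR) × uptake in non-responders.

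| Assumed uptake, responders / non-responders | Arm uptake, pRR 75% v 50% | Mean window (days) | Gap (days) |
|---|---|---|---|
| 50% / 50% | 50% v 50% | 100.5 v 100.5 | 0 |
| 30% / 90% | 45% v 60% | 104.0 v 93.6 | 10.4 |
| 20% / 100% | 40% v 60% | 107.4 v 93.6 | 13.8 |

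**Position of the 12-week summary.** Counted from first dose, 12 weeks end on Day 84, one day before the earliest on-schedule adjuvant start (Day 85). An adjuvant start on schedule does not cut it.

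**The case against.** **The plan already has a fixed window and shows follow-up.** The 12-week summary by arm ends before adjuvant therapy and targets the main risk of these drugs. Length of safety follow-up is also tabulated by arm, so unequal observation would be visible. This stands in part: the 12-week summary is limited to Grade ≥3 immune-related events, and displaying follow-up does not adjust for it.

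**Reporting does not stop.** A reader might infer that SAE reporting ceases at adjuvant start. Section 5.6 does not support that: related SAEs and all deaths remain reportable, and the hold criteria in Section 3.1.3 rest on treatment-related events and deaths. What remains of the concern is a change of method, from causality-blind collection to reports filtered by awareness and believed relatedness. That filter is harder to apply once an adjuvant drug offers another explanation.

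**Selection on response is not a rule.** A reader might infer that responders are observed and non-responders treated, so that arms with more responders must look more toxic. Section 1.1.2.1 calls pathologic response "valuable to estimate prognosis and to guide the choice of adjuvant therapy and follow-up", but that is background on neoadjuvant therapy. Section 3.4.4 says only that the approach could guide adjuvant use. The operative rule is investigator discretion.

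**A bias of several points is a worst case.** With an assumed 10% risk of a late event and pRR of 80% v 50%, complete separation by response and no capture under Section 5.6 give 0.8 × 10% = 8% v 0.5 × 10% = 5%, or 3 points. Uptake of 20% / 100% in responders / non-responders gives 2.4 points, 30% / 90% gives 1.8, and equal uptake gives 0. Three points is 0.6 to 1.8 patients in arms of 20–60.

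**Expansion is largely untouched.** The earliest interim analysis (Section 6.9) follows pathologic assessment at about Week 7, before late events exist for recent enrollees. No formal comparison of 600 mg with 2100 mg is specified either.

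**Stopping at new therapy has a purpose.** Adjuvant anti-PD-1 belongs to the same toxicity class, so longer collection would import its events.

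The last four objections limit the size and reach of the point. They do not supply a common cut-off for SAEs and AESIs.

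**Conclusion.** The point holds as a gap in the analysis rule. For two-dose patients who start systemic adjuvant therapy on schedule, routine SAE/AESI collection covers 63–69 of 135 days, about half. This follows from the documents, provided adjuvant therapy counts as new systemic therapy; the text reads that way but does not say so. Unequal windows between patients are certain wherever adjuvant use varies.

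Unequal windows between arms are conditional on adjuvant uptake differing by arm. The gap is zero with equal uptake and about 10–14 days in the mean window under strong assumed selection by response. Neither the direction nor the size of any bias in a given arm can be stated from the documents. The study specifies no formal safety test, so the effect falls on descriptive benefit–risk reading. This is a cheap improvement, not a flaw that undermines the design.

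The arm-specific schedules of activities (A11–6 onward) were not in the text available to me, so their adverse event footnotes are unchecked.

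**What to change.** 1. **Section 6.5, between-arm table.** For Cohort 1, base the SAE/AESI comparison on one fixed window for all patients, first dose to Day 84. This matches the 12-week window already used for immune-related events and precedes any on-schedule adjuvant start. Flag patients who start new therapy earlier, for example after progression before surgery.
2. **Section 6.5, full-period table.** Show SAEs and AESIs over the whole reporting period separately, with follow-up time or exposure-adjusted rates. List events reported under Section 5.6 after adjuvant start apart from the rest.
3. **Section 5.3.1.** State that adjuvant therapy counts as new systemic anti-cancer therapy, if that is intended, and carry the wording into Sections 5.4.2.2 and 5.6.

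**Cost.** One extra table and a sentence of protocol text. No new data are needed, since new anti-cancer therapy is already recorded during follow-up (Section 4.6.1). The fixed-window table omits events after Day 84, which is why the second table is needed. Exposure-adjusted rates assume a roughly constant event rate, so they help with the late period but do not fully correct it.

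Continuing SAE/AESI collection through adjuvant therapy, with a flag for onset after adjuvant start, is optional. It would recover late events but add events caused by the adjuvant drug.
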